6.3.1.6 Sensitivity Analysis

Observed Case Analysis

The robustness of the LOCF approach for missing data will be addressed by completing a sensitivity analysis. This will be an observed case analysis of the endpoints described in Sections 6.3.1.1 to 6.3.1.5, with no imputation methods for missing data, in order to assess the robustness of the primary efficacy results.

Mixed Model for Repeated Measures Analysis

As additional sensitivity analyses, the endpoints described in **Sections 6.3.1.1 to 6.3.1.5** will each be analyzed using a mixed effects model for repeated measures (MMRM) on the ITT population. The models will include treatment, visit, treatment-by-visit interaction, country and Baseline value as fixed effects, and will use an unstructured (general) residual covariance matrix for repeated records within subjects. For each endpoint, the LS mean change in the endpoint from Baseline will be presented for each treatment by visit and overall, along with the corresponding SE. The difference in LS means (0.005% Estriol versus Placebo, 0.002% Estriol versus Placebo and 0.0008% Estriol versus Placebo) will also be presented with 95% CI and one-sided p-value for each visit and overall. The p-values will also be presented for the model parameters of visit, treatment-by-visit interaction, country and Baseline value.

Only ITT population subjects with both a Baseline and at least one post-Baseline measurement for a given endpoint will be included in the MMRM for that endpoint.

Due to the categorical nature of the vaginal dryness endpoint, the change from Baseline (Screening) vaginal dryness values and the Baseline (Screening) vaginal dryness values will be assigned ranks according to their order within each treatment group, and the MMRM will be conducted on the ranked values.

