Estriol formulations have been marketed since 1958 for the treatment of vulvovaginal atrophy in more than 50 countries worldwide, including all European countries, but not the United States. Topical (vaginal) formulations are currently available as creams (containing 1 mg estriol/1 g cream) or as ovules (containing 0.5 mg estriol). Local vaginal estrogen therapy can also be administered in the form of estradiol vaginal tablets or vaginal creams, estradiol-releasing vaginal rings and conjugated estrogen-based vaginal creams.

The search for therapeutic alternatives, which may present improvements in relation to the current products, has been encouraged. In response to this need, ITF Research Pharma SLU has developed a 0.005% estriol vaginal gel; this estriol-based formulation for intravaginal application uses a dose of the hormone ten times lower than that included in currently marketed vaginal estriol products. It proved to be an effective treatment for postmenopausal vaginal atrophy, as the majority of symptoms and signs of postmenopausal vaginal atrophy were improved after

treatment, with improvement evidenced in as little as 3 weeks after treatment initiation. A favorable safety profile was demonstrated, as systemic exposure to estriol was shown to be extremely low after repeated administration and no differences in the adverse event (AE) profile (type and severity) were demonstrated when compared to placebo treatment (Cano A, 2012). While maintaining efficacy, the reduced estrogen exposure results in a more favorable risk/benefit ratio for the patient. This new formulation consists of a muco-adhesive gel with pleasant pharmaceutical properties (freshness, cleanliness, odorless) and easy application. These aspects are considered relevant as specialties in the market for the treatment of vaginal atrophy are often perceived as unpleasant to use by some patients and may result in discontinuation of treatment. The gel also has a hydrating effect, which may additionally contribute to the relief of some of the characteristic symptoms of atrophy.

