6.3.1.5 Gatekeeping Procedure

For the co-primary efficacy endpoints, a gatekeeping procedure will be employed. The 0.005% Estriol dose will be compared to placebo, and if this is significant at a one-sided alpha level of 0.025 for all four co-primary endpoints, then the 0.002% Estriol dose versus placebo can be considered. If this is also significant at a one-sided alpha level of 0.025 for all four co-primary endpoints, then the 0.0008% Estriol dose versus placebo can be considered. The approach to be taken is outlined in Table 4 below.

The one-sided p-values for all four co-primary endpoints will be presented for all three treatment comparisons in an overall gatekeeping table, so that it may be clearly seen whether or not all four co-primary endpoints are statistically significant and therefore be determined for which treatment comparisons efficacy can be formally declared. The overall gatekeeping table will be presented using the ITT population with LOCF methodology for the co-primary efficacy analyses, and also

using observed data only for the PP population and the ITT population in order to confirm the co-primary efficacy results.

Table 4: Gatekeeping Procedure for Efficacy Analyses

Test	Endpoints	All endpoints significant	Result	Next step
0.005% Estriol versus placebo	Vaginal dryness Vaginal pH Superficial cells Parabasal cells	Yes	If treatment difference exists between 0.005% Estriol and placebo, move to next dose	Continue to test 0.002% Estriol versus placebo
	Vaginal dryness Vaginal pH Superficial cells Parabasal cells		Not enough evidence to conclude a difference exists between 0.005% Estriol and placebo	Stop testing
0.002% Estriol versus placebo	Vaginal dryness Vaginal pH Superficial cells Parabasal cells	Yes	If treatment difference exists between 0.002% Estriol and placebo, move to next dose	Continue to test 0.0008% Estriol versus placebo
	Vaginal dryness Vaginal pH Superficial cells Parabasal cells		Not enough evidence to conclude a difference exists between 0.002% Estriol and placebo	Stop testing
0.0008% Estriol versus placebo	Vaginal dryness Vaginal pH Superficial cells Parabasal cells	Yes	Treatment difference exists between 0.0008% Estriol and placebo	Stop testing
	Vaginal dryness Vaginal pH Superficial cells Parabasal cells		Not enough evidence to conclude a difference exists between 0.0008% Estriol and placebo	Stop testing

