6.8 Changes to Methods Planned in the Protocol

- Section 6.2.3.3 of the protocol Version 5.0 describes the Global Symptom Score as the sum of the numerical scores of all five symptoms of vulvovaginal atrophy at a given time point, and states that this score will be evaluated only when all five individual symptoms scores are available. This Global Symptom Score is identified in this Statistical Analysis Plan (SAP) as Global Symptom Score 1, and is analyzed as described in **Section 6.3.2.5**, and as planned in the protocol. This score is labeled as Global Symptom Score 1 in order to distinguish it from the alternative score described in the following bullet.
- The Global Symptom Score 1 requires all five individual symptoms to have a response available. Given that the dyspareunia symptom is only applicable in subjects who experienced sexual activity with penetration since the previous study visit, it is acknowledged that there may be a considerable number of subjects / time points where the Global Symptom Score 1 is not available. In order to allow a Global Symptom Score analysis that utilizes as many subjects as possible, an additional score has been defined that was not planned in the protocol Version 5.0. The Global Symptom Score 2 is defined as the sum of the four individual symptoms excluding dyspareunia, requires all 4 of these symptoms to be available, and is analyzed as described in **Section 6.3.2.6**.
- Although not required by the protocol, additional exploratory ANCOVA analyses are planned for the mean maturation values from the vaginal smear samples. The change from Baseline to Week 12 and the change from Baseline to Week 3 will be analyzed using the same ANCOVA approach described in the for the percentage of superficial cells and the percentage of parabasal cells. The analyses of these additional parameters have been included because they are considered to be relevant.

- Additional sensitivity MMRM analyses are planned for the four co-primary efficacy endpoints. These extra analyses have been added for the purposes of robust exploratory comparison against the LOCF approach used for the primary analyses.

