7.2.2 Efficacy Data

Table 14.2.1.1.1	Co-Primary Efficacy Analysis of Change from Baseline to Week 12 in Severity of Vaginal Dryness (LOCF)	ITT Population
Table 14.2.1.1.2	Analysis of Change from Baseline to Week 12 in Severity of Vaginal Dryness	PP Population
Table 14.2.1.1.3	Sensitivity Analysis of Change from Baseline to Week 12 in Severity of Vaginal Dryness (Observed Case)	ITT Population
Table 14.2.1.1.4	Sensitivity Analysis of Change from Baseline in Severity of Vaginal Dryness (MMRM)	ITT Population
Table 14.2.1.2.1	Co-Primary Efficacy Analysis of Change from Baseline to Week 12 in Vaginal pH (LOCF)	ITT Population

STATISTICAL ANALYSIS PLAN
 ITF Research Pharma SLU
 ITFE-2092-C1
 Page 54

Table 14.2.1.2.2	Analysis of Change from Baseline to Week 12 in Vaginal pH	PP Population
Table 14.2.1.2.3	Sensitivity Analysis of Change from Baseline to Week 12 in Vaginal pH (Observed Case)	ITT Population
Table 14.2.1.2.4	Sensitivity Analysis of Change from Baseline in Vaginal pH (MMRM)	ITT Population
Table 14.2.1.3.1	Co-Primary Efficacy Analysis of Change from Baseline to Week 12 in Proportion of Superficial Cells of the Vaginal Epithelium (LOCF)	ITT Population
Table 14.2.1.3.2	Analysis of Change from Baseline to Week 12 in Proportion of Superficial Cells of the Vaginal Epithelium	PP Population
Table 14.2.1.3.3	Sensitivity Analysis of Change from Baseline to Week 12 in Proportion of Superficial Cells of the Vaginal Epithelium (Observed Case)	ITT Population
Table 14.2.1.3.4	Sensitivity Analysis of Change from Baseline in Proportion of Superficial Cells of the Vaginal Epithelium (MMRM)	ITT Population
Table 14.2.1.4.1	Co-Primary Efficacy Analysis of Change from Baseline to Week 12 in Proportion of Parabasal Cells of the Vaginal Epithelium (LOCF)	ITT Population
Table 14.2.1.4.2	Analysis of Change from Baseline to Week 12 in Proportion of Parabasal Cells of the Vaginal Epithelium	PP Population
Table 14.2.1.4.3	Sensitivity Analysis of Change from Baseline to Week 12 in Proportion of Parabasal Cells of the Vaginal Epithelium (Observed Case)	ITT Population
Table 14.2.1.4.4	Sensitivity Analysis of Change from Baseline in Proportion of Parabasal Cells of the Vaginal Epithelium (MMRM)	ITT Population
Table 14.2.1.5.1	Gatekeeping Table for Co-Primary Efficacy Analysis of Change from Baseline to Week 12 (LOCF)	ITT Population
Table 14.2.1.5.2	Gatekeeping Table for Analysis of Change from Baseline to Week 12	PP Population

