Table 14.2.1.5.3	Gatekeeping Table for Sensitivity Analysis of Change from Baseline to Week 12 (Observed Case)	ITT Population
Table 14.2.1.5.4	Gatekeeping Table for Sensitivity Analysis of Change from Baseline to Week 12 (MMRM)	ITT Population
Table 14.2.2.1	Analysis of Change from Baseline to Week 3 in Severity of Vaginal Dryness	ITT Population
Table 14.2.2.2.1	Analysis of Change from Baseline to Week 12 in Severity of Dyspareunia (LOCF)	ITT Population
Table 14.2.2.2.2	Analysis of Change from Baseline to Week 3 in Severity of Dyspareunia	ITT Population
Table 14.2.2.3.1	Analysis of Change from Baseline to Week 12 in Severity of Pruritus or Itching (LOCF)	ITT Population
Table 14.2.2.3.2	Analysis of Change from Baseline to Week 3 in Severity of Pruritus or Itching	ITT Population

STATISTICAL ANALYSIS PLAN
 ITF Research Pharma SLU
 ITFE-2092-C1
 Page 55

Table 14.2.2.4.1	Analysis of Change from Baseline to Week 12 in Severity of Burning (LOCF)	ITT Population
Table 14.2.2.4.2	Analysis of Change from Baseline to Week 3 in Severity of Burning	ITT Population
Table 14.2.2.5.1	Analysis of Change from Baseline to Week 12 in Severity of Dysuria (LOCF)	ITT Population
Table 14.2.2.5.2	Analysis of Change from Baseline to Week 3 in Severity of Dysuria	ITT Population
Table 14.2.2.6.1	Analysis of Change from Baseline to Week 12 in Global Symptom Score 1 (LOCF)	ITT Population
Table 14.2.2.6.2	Analysis of Change from Baseline to Week 3 in Global Symptom Score 1	ITT Population
Table 14.2.2.7.1	Analysis of Change from Baseline to Week 12 in Global Symptom Score 2 (LOCF)	ITT Population
Table 14.2.2.7.2	Analysis of Change from Baseline to Week 3 in Global Symptom Score 2	ITT Population
Table 14.2.2.8.1	Summary of Symptoms of Vulvovaginal Atrophy by Treatment and Visit	ITT Population
Table 14.2.2.8.2	Summary of Global Symptom Score 1 and 2 by Treatment and Visit	ITT Population
Table 14.2.3.1.1	Analysis of Change from Baseline to Week 12 in Severity of Pallor (LOCF)	ITT Population
Table 14.2.3.1.2	Analysis of Change from Baseline to Week 3 in Severity of Pallor	ITT Population
Table 14.2.3.2.1	Analysis of Change from Baseline to Week 12 in Severity of Friability (LOCF)	ITT Population
Table 14.2.3.2.2	Analysis of Change from Baseline to Week 3 in Severity of Friability	ITT Population
Table 14.2.3.3.1	Analysis of Change from Baseline to Week 12 in Severity of Thinning or Flattening of Folds (LOCF)	ITT Population

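### Ranking vaginal dryness within each arm before the MMRM removes the estriol–placebo comparison that the model is meant to estimate

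*SAP*

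**What the plan says.** SAP 6.3.1.6 adds an MMRM on the ITT population for each co-primary endpoint: "The models will include treatment, visit, treatment-by-visit interaction, country and Baseline value as fixed effects", with an unstructured covariance. Each estriol dose is to be compared with placebo by a difference in LS means, which "will also be presented with 95% CI and one-sided p-value for each visit and overall".

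Because dryness is categorical, its changes from Baseline and its Baseline values "will be assigned ranks according to their order within each treatment group, and the MMRM will be conducted on the ranked values". The SAP does not say whether ranks are taken separately at each visit or over both visits together. The pH, superficial-cell and parabasal-cell models use unranked values.

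SAP 7.2.2 plans a dryness MMRM table (14.2.1.1.4) and an MMRM version of the gatekeeping table (14.2.1.5.4). Under SAP 6.3.1, efficacy needs all four endpoints to be significant. SAP 6.8 gives the purpose: "These extra analyses have been added for the purposes of robust exploratory comparison against the LOCF approach used for the primary analyses".

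**The concern.** The two instructions defeat each other. Ranking inside each arm puts every arm on its own scale with the same centre, and the model is then asked how far apart the centres are. Baseline is ranked the same way, so covariate adjustment cannot bring the difference back.

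The outputs are prespecified and would be read as a check on LOCF. With equal arms ranked by visit, the MMRM gatekeeping table would stop at 0.005% whatever the truth and would seem to contradict a positive primary result. With unequal arms it could lend false support or point towards placebo. For dryness, this MMRM is the only model-based check on LOCF.

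**Working it through.** **Inputs.** Table 2 (SAP 6.1.4), changes −3, −2, −1, 0, +1: estriol 0.189, 0.423, 0.270, 0.118, 0; placebo 0.118, 0.196, 0.353, 0.333, 0. Also 57 per arm, 18% drop-out, about 70 per arm, one-sided 0.025.

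**The plan's own figure.** P(estriol better) = 0.189×0.882 + 0.423×0.686 + 0.270×0.333 = 0.5468. P(tie) = 0.2398. The sum 0.5468 + 0.2398/2 is 0.667. The tie-corrected rank-sum calculation gives 90.7% power at 57 per arm, and simulation gives 90.5%. 57/(1 − 0.18) = 69.5, rounded to 70. The sample size reproduces and is not in dispute.

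**The identity.** Mid-ranks of n values sum to n(n+1)/2, so their mean is (n+1)/2. If all three women in one arm change by −3, each has mid-rank 2; if all three in another arm change by 0, each also has mid-rank 2. The difference in mean ranks is (n_E − n_P)/2, whatever the outcomes.

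**Simulation of the stated MMRM.** Four arms, Weeks 3 and 12, the SAP's fixed effects, unstructured covariance, 1,000 runs per scenario, 0.005% against placebo at Week 12. Assumptions not in the documents: half severe at Baseline (range 0.3 to 0.7), within-subject latent correlation 0.5 (0.3 to 0.7), five equal countries with no country effect, all estriol arms following the estriol column, half of any losses before Week 3.

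| Scenario | Ranked within arm, by visit | Ranked across arms |
|---|---|---|
| Table 2 effect, 57 per arm | contrast 0.0, 0.0% significant | 92.4% (90.6% to 96.5%) |
| Table 2 effect, 70 per arm | contrast 0.0, 0.0% | 97.0% |
| Table 2 effect, 70 per arm, independent 18% loss | 2.3% | 91.4% |
| No effect, 65 estriol v 70 placebo | contrast −3.1, 0% | – |
| No effect, 60 estriol v 70 placebo | contrast −6.2, 31% | 2.3% |
| Table 2 effect, 70 estriol v 60 placebo | contrast +6.7, towards placebo in every run | – |

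A second simulation used 2,000 runs, a Week 3 effect of 60% of the Week 12 effect, visit correlation 0.6, 45% severe and complete data. At 70 per arm it gave a contrast of 0.01 and 0.0% within arm, against 96.4% across arms. Over all assumption sets tried, across-arm ranking gave 88% to 97% at 57 or 70 per arm. Its one-sided rejection rate with no effect was 2.1% to 3.6%.

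**Why 60 v 70 gives −6.2 and not −5.** The mean-rank difference is (61 − 71)/2 = −5. The Baseline ranks differ by −5 as well, so with Baseline slope b the adjusted contrast is −5(1 − b); −6.2 implies b = −0.24. The same b gives −2.5×1.24 = −3.1 at 65 v 70, as simulated.

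**How firm is the 31%?** Ignoring ties, the rank variance in an arm is (n² − 1)/12: 299.9 at 60 and 408.3 at 70. The SE is √(299.9/60 + 408.3/70) = 3.29. With the placebo proportions the tie factor is √(1 − 0.090) = 0.954, giving 3.14, so significance needs about 1.96×3.14 = 6.2 ranks. The contrast sits on that line, so the percentage moves with small modelling choices: other runs gave 29% to 61%. The contrast is the stable figure.

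**No effect, non-differential loss.** With 70 randomised and 18% independent loss, the SD of the evaluable number is √(70×0.18×0.82) = 3.21 per arm, and 4.55 for the difference between two arms. The contrast then has SD 4.55/2×1.24 = 2.8 ranks. At about 57 per arm the threshold is 1.96×√(270.7×2/57)×0.954 = 5.8 ranks. The ratio 5.8/2.8 is about 2, a tail of about 2%, as simulation also found.

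**Ranks pooled over both visits within an arm.** Only a difference in time course survives. If the effect is equal at both visits, significance is 0.0% at 57 and at 70 per arm (up to 0.4% over the assumption range). If the Week 3 effect is 60% of the Week 12 effect, it is 1.3% at 57 and 2.1% at 70. If the whole effect arises after Week 3, it is 51%, against 97.6% across arms.

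**The case against.** **No decision rests on it.** This stands. The protocol does not plan an MMRM, and SAP 6.8 calls it exploratory. SAP 6.3.1.5 bases efficacy on ITT with LOCF and adds gatekeeping tables "using observed data only for the PP population and the ITT population in order to confirm the co-primary efficacy results"; the MMRM is not among them.

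**SAP 6.1.1 allows an unsuitable method to be replaced.** It does, with the change and rationale reported in the CSR, and a contrast of zero would be noticed. But the final analysis follows unblinding, so the ranking rule would be rewritten with treatment codes known. With unequal arms the fault may not be obvious. The Appendix I table shells are not in the available text and might say more.

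**False significance needs differential loss.** This stands. With independent 18% loss and no effect the rate is about 2%, below nominal. Early Termination assessments of dryness, if analysed as Week 12 values, would bring evaluable numbers closer still. The loss of information remains: with equal arms the row is empty.

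**Pooling visits keeps some power.** It does if the effect arises late. SAP section 1 reports improvement in most symptoms and signs, "with improvement evidenced in as little as 3 weeks after treatment initiation". That does not name dryness or give a Week 3 difference from placebo, so it is only modest support for an early effect. Still, an analysis that detects only a late effect does not check the Week 12 result.

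**Conclusion.** The concern holds. Within-arm ranking by visit makes the dryness contrast a function of arm size alone, apart from small covariate adjustments. This is an identity and needs no simulation assumption. Its practical size is 0.0% significance with equal arms of 57 or 70 under the Table 2 effect, against 88% to 97% with across-arm ranks. With a 10-woman imbalance, a contrast of 6 to 7 ranks arises from arm size and can run against the true effect. The percentages rest on the assumed Baseline severity, within-subject correlation and country structure, and the false-significance rate at 60 v 70 (29% to 61%) is especially sensitive. Pooling visits avoids the problem only in part, when the effect arises largely after Week 3.

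The reach is limited to Table 14.2.1.1.4 and to the dryness row and all-four verdict of Table 14.2.1.5.4. It should be corrected, but it does not threaten the trial's primary conclusion.

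**What to change.** Before unblinding, amend SAP 6.3.1.6 so that dryness changes are ranked *across all treatment groups combined, separately at each visit, with mid-ranks for ties*, and Baseline dryness is ranked across all groups combined. Then fit the MMRM as already specified.

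Ranking within each estriol–placebo pair, as the pairwise Wilcoxon test does, is also legitimate. It gives each placebo subject three different ranks, so it needs three separate models in place of the single model stated, and it was not simulated here. The across-all-groups rule is simpler and is the one supported by the figures above.

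The cost is one phrase in the SAP and one line in the ranking step, with no effect on data collection or patients.

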6.3.2 Secondary Efficacy Analysis

The secondary efficacy analyses will be performed using the ITT population. Secondary efficacy endpoints include the change from Baseline to Week 12 in the severity of individual symptoms (excluding vaginal dryness, i.e. dyspareunia, pruritus or itching, burning, and dysuria) and signs of vulvovaginal atrophy (pallor, friability, thinning or flattening of folds, presence of petechiae, and dry mucosa) and global symptom scores, as well as the change from Baseline to Week 3 in the severity of individual symptoms (as above, include vaginal dryness) and signs and global symptom scores, vaginal pH and proportions of superficial and parabasal cells, respectively. The planned analyses of each of these endpoints are described in **Sections 6.3.2.1 to 6.3.2.26** below.

6.3.2.1 Change from Baseline to Week 12 in Severity of Dyspareunia

Dyspareunia is one of the five symptoms of vulvovaginal atrophy. It is self-assessed by the subject at the Baseline, Week 3 and Week 12 / Early Termination visits, and is scored using a numeric scale from 0 to 3 as described in **Section 6.3.1.1**. Dyspareunia is only applicable in subjects who have experienced sexual activity with penetration since the previous study visit.

The number and percentage of subjects with each severity of dyspareunia at each visit will be summarized by treatment in a general summary table of symptoms of vulvovaginal atrophy.

The change from Baseline to Week 12 in severity of dyspareunia may take the possible values ranging from -3 (Severe at Baseline, Absent at Week 12) to 3 (Absent at Baseline, Severe at Week 12). The change from Baseline in severity of dyspareunia will only be calculated when the

subject has indicated that they have experienced sexual activity with penetration at both the Baseline and the post-Baseline visit. This endpoint will be summarized and analyzed as described for vaginal dryness in **Section 6.3.1.1**. Missing values at Week 12 will be estimated using LOCF methodology. Only post-Baseline values will be carried forward.

